After informed consent is received, a neurological examination will be performed and multiple screening assessments will be conducted including a tDCS and MRI safety screening (see below). If the participant passes the initial screening portion, speech and language diagnostic testing will be conducted during the same visit (Visit 1). During the next visit (Visit 2), participants will undergo a second baseline assessment of naming ability and assessment of connected speech. On that visit, participants who have no contraindication for MRI will be randomized to (1) fMRI electrode placement or (2) structural electrode placement. All participants who have no contraindication will have structural and rsfcMRI. Those randomized to fMRI electrode placement will also participate in the naming paradigm. Those who agree will also undergo fNIRS. The third visit will include electrode positioning and tDCS treatment administration. Participants will receive 15 sessions (Visits 3-17) of tDCS treatment administration. At the beginning of Visit 3, eligible participants will be randomized to receive either A-tDCS (1 mA) or sham-tDCS (placebo) for 15 sessions (20-minutes per each 45-minute behavioral treatment session) over the course of three weeks. A computer-delivered naming treatment will be coupled with the stimulation. The computer-delivered treatment task will be 45-minutes in total length, so that it will commence at the same time as the tDCS administration and continue for another 25-minutes after the tDCS has ceased.

c. Blinding, including justification for blinding or not blinding the trial, if applicable.

Randomization and Blinding

The study is to be conducted in a double-blind manner. The subjects, the site investigators, and the clinical staff involved in this study will not know the treatment assignment. Select members of the statistical and Data Management Center will be partially blinded, i.e., they will know the treatment group assignment as A or B, but not whether the patient receives active tDCS or sham. The study statistician and the DSMB will have a sealed envelope with the treatment group identifiers. This envelope would only be opened if the study statistician is directed to open it by the DSMB or at the end of the futility study.

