The randomization will take place centrally via the Trial Website. Subjects will be randomized 1:1 (A-tDCS: S-tDCS), controlling for clinical center, aphasia type, and severity (classified using the Western Aphasia Battery revised: WAB-R). The computer program developed at the DCU makes the treatment assignment based on the current status of treatment group distribution within each stratum as well as overall balance of treatment assignment. The randomization scheme will never be deterministic. The detailed randomization scheme and source codes will be provided in the Randomization Plan document.

A "Real-Time" randomization procedure is implemented via the Trial Website on the WebDCU™

Date: March 2, 2021

Principal Investigator: [name], MA

Application Number: IRB00089018

System where the clinical center staff enters the basic baseline (e.g. aphasia type, and AQ severity) and eligibility information of a subject prior to enrollment. If the subject's eligibility status is confirmed, the computer program on the WebDCU™ server will evaluate the treatment arm distribution and generate a patient number based on the randomization scheme. The SLP enrolling the patient will not see the treatment assignment, only a numeric patient number which is entered into a software package that controls whether the tDCS given is A-tDCS or Sham. In order to mask treatment type (A-tDCS vs. Sham) for both patients as well as the SLPs administering the treatment session (i.e., setting up the tDCS and starting and monitoring the computerized treatment task), we use in-house software/hardware. As previously discussed, this setup allows for switching the tDCS on and off without any involvement from the patient or experimenter. The software is run on a lap-top computer connected to the tDCS stimulator. Treatment type is encoded in the software so that the administrator only needs to enter a patient and session number to start stimulation without knowing whether those specific numbers are associated with A-tDCS or Sham. The unblinded list of randomization codes and treatment assignments will be generated by the DCU and will be uploaded into the software by a software administrator who is not otherwise involved in the study.

d. Justification of why participants will not receive routine care or will have current therapy stopped

Participation in this study will not disrupt any current care or therapy.

e. Justification for inclusion of a placebo or non-treatment group

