The primary analysis will compare change in accuracy of naming untrained items between groups (A-tDCS versus sham) in a two-sample *t*-test for the Intent-to-treat sample. For participants who do not complete the Week 1 post-treatment assessment, the post-treatment value will be imputed using a multiple imputation approach assuming a monotone missing mechanism and missing is at random (MAR). As a sensitivity analysis, the primary outcome analysis will be repeated using all available follow-up data (without explicit imputation) in a mixed effects model of the change from baseline in naming accuracy adjusted for baseline (with Week 1, 5, or 20 as a categorical variable and a random effect for subject). Similar analyses will be done for the change in accuracy of trained items.

If we accept the null hypothesis, then tDCS is considered clearly ineffective (in improving anomia in stroke patients) and will not be considered for further study. If we reject the null hypothesis, we would consider undertaking a Phase III study of tDCS.

Sample Size Determination

We expect to enroll 50 participants over 4 years, and expect 40-45 will complete the study. We predict no difficulty recruiting at least 10-15 participants with aphasia each year after subacute stroke, as the PI has

Date: March 2, 2021

Principal Investigator: [name], MA

Application Number: IRB00089018

recruited an average of 53 aphasic patients due to acute left hemisphere ischemic stroke each year in her previous studies of aphasia recovery. If sample size in each group is 20, (a total sample size of 40), we will have 89% power to detect a difference in means of 23 (the difference between a A-tDCS mean change in accuracy, μ_1 , of 33 and a sham mean change in accuracy, μ_2 , of 10) assuming that the standard deviation of change for both groups is 22.2 using a two group *t*-test with a two-sided alpha of 0.05. These mean changes for tDCS and sham and standard deviation of change are based on the one published sham-controlled study of tDCS combined with SALT in subacute stroke.

Multiplicity

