Since this is a Phase I/II study, the false positive error rate has been relaxed (Schoenfeld, 1980). For a futility design the type I and type II error rates are reversed as compared to a traditional, superiority hypothesis. For the primary analysis, the probability of incorrectly declaring a drug futile is 0.1 (or 10%, type I error is the false negative rate). Given that the active tDCS comes from a distribution with a mean change of the control group (e.g. the treatment is the same as the sham), the probability of incorrectly moving to a Phase III trial is 0.15 (or 15%, type II error is the false positive rate).

For secondary outcomes and safety analyses, no adjustment of Type I error probability will be considered, since they will be treated as exploratory.

Missing Data

Under the ITT principle, all patients who are randomized are included in the analysis. Therefore, missing data, especially in the primary outcome measure, can be problematic. For the primary futility analysis we will impute missing data using multiple imputation (Rubin, 1987) assuming a monotone missing mechanism and missing is at random (MAR). Similar methods will be employed for secondary analyses and secondary outcomes. For safety data (e.g. AEs) no data imputation will be done.

Interim Analysis

No formal interim analyses are planned.

Adjusting for Covariates

The primary analysis will be adjusted for aphasia type, and baseline aphasia severity (AQ), education, time from stroke onset to time of treatment initiation, and number of previous SLP treatment sessions (prior to our study).

Secondary Analyses

In addition to the primary outcome, several secondary analyses will be conducted. We will examine changes in types of naming errors (defined by the PNT) by tDCS treatment group. The Cinderella story will be analyzed by comparing lexical diversity (VOCD) for nouns, verbs and adjectives; number and types of errors; length and patterns of pauses by treatment group. Pre and post comparisons with both non-aphasic and aphasic speakers from the Aphasia Bank database who share a number of demographic features (e.g., type and severity of aphasia, age, etc.) will also be made. We will also evaluate differences between treatment groups in QOL as measured by the Stroke Impact Scale, mRS, Content Units (CU) and syllables/CU in describing the Cookie Theft picture on the NIH Stroke Scale.

At the end of the study, for the interval scale variables, mean change from baseline to immediate

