Date: March 2, 2021

Principal Investigator: [name], MA

Application Number: IRB00089018

post-testing in secondary outcome measures will be reported by treatment group along with the 95% confidence intervals. Treatment comparisons will be made with a paired t- test. For binary variables, the proportion of subjects immediately post-testing will be reported by treatment group along with the 95% confidence intervals.

Post-Testing Phase

The longer follow-up post-testing phase will provide exploratory information on whether the immediate post-testing improvement after three weeks of treatment can be sustained. The mean (95% CI) changes from baseline to immediate (within one week) post-testing, five weeks (after the end of treatment) post-testing and 20 weeks (after the end of treatment) post-testing will be reported. Box and whisker plots will be produced to show the distribution of naming accuracy over time by treatment group. To explore the longitudinal data, a general linear mixed model (GLMM) will be constructed by tDCS group for the dependent variable (anomia). The GLMM will incorporate random subject effects to account for repeated measurements being made on subjects; the model will include time, aphasia type, severity, and clinical center as independent variables. A similar modeling approach may be applied to other secondary outcomes.

Safety Analyses

All adverse experiences will be summarized in terms of frequency, severity and relatedness to the study treatment using the MedDRA code. All subjects who received tDCS will be included in the safety analysis. At the end of the study, the cumulative incidences of adverse events are compared between the two treatment groups using Fisher's exact test at the two-sided alpha level of 0.05.

The repeated measures of the FACES pain rating scale will be compared by treatment group by fitting a repeated measures proportional odds model.

DSMB Reporting

The study biostatistician will generate closed and open DSMB reports semi-annually or more frequently, as determined by the DSMB. Each DSMB report provides cumulative summary statistics on enrollment; subject status in the study (e.g., number completed study, drop outs, etc.); baseline characteristics; safety data, including AEs and SAEs; and data quality information. The statistics for the closed DSMB Reports are provided by treatment group displayed as A or B. The open report contains aggregated statistics only, i.e., not by treatment group.

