2. STATISTICAL ANALYSIS PLAN AND STATISTICAL REPORTS

This document provides the details of the statistical analyses planned for the trial. Prior to locking the database and breaking the code, this Statistical Analysis Plan (SAP) will be updated. The final SAP will define all “pre-specified, pre-planned analyses” and will trump the protocol.

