8.2 Statistical Hypotheses

The Primary Hypothesis 1a: A-tDCS over a targeted region coupled with computer-delivered SALT is associated with greater gains in accuracy in naming pictures, compared to sham coupled with the same computer-delivered SALT in post stroke aphasia. To test this hypothesis, we will compare the change in means of outcome measures in the group who received sham versus the group who received tDCS. The primary outcome variable will be change in accuracy of naming untrained items within one week after treatment ends. The null hypothesis is $H_0: \mu_1 = \mu_2$, where μ_1 is the mean change in accuracy of naming untrained items (PNT correct) between baseline and 1 week post-treatment in the A-tDCS group and μ_2 is the mean change in the sham group. The primary analysis will compare change between groups (A-tDCS versus S-tDCS) using multiple regression and will be adjusted for aphasia type (Anomia, Broca, or other type), baseline aphasia severity (AQ), and age. The primary analysis will be performed using both the Completers and Modified Intent-to-treat Samples. If these two analyses are not consistent, then the trial findings will be interpreted with caution.

Sensitivity analyses will be done for the change in accuracy of trained items using the same approach. Naming errors will also be analyzed and categorized as semantic related, semantic unrelated, real words related phonologically, non-words related phonologically, mixed semantic/phonological, abstruse neologisms, and no response. Additional sensitivity analyses will adjust for education and time from stroke onset to time of treatment initiation in addition to the covariates included in the primary model.

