10. SECONDARY ANALYSES

Secondary analyses will evaluate the effect of A-tDCS vs sham on change in lexical features of discourse, Content Units (CU) and syllables/CU in describing the Cookie Theft picture, HANA, NIH Stroke Scale, SIS, mRS, and PHQ-9.

For continuous measures, the secondary analyses will be adjusted for aphasia type (Anomia, Broca, or other type), baseline aphasia severity (AQ), and age using a linear mixed effects regression to compare treatment groups. The model will include repeated measures of change from baseline to 1, 5, 20 weeks post and visit will be a classification variable with interaction terms for visit*treatment group (SAS PROC MIXED with a REPEATED subcommand).

```
PROC MIXED;
  CLASS SUBJID ARM VISITNUM TYPE;
  MODEL CHANGE= ARM|VISITNUM WABAQ TYPE AGE;
    REPEATED VISITNUM / TYPE= CS SUBJECT=SUBJID R RCORR;
  LSMEANS ARM*VISITNUM/pdiff CL;
RUN;
```

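### The protocol names a paired t-test for comparing two independent randomised arms, and for naming-error types it is the only between-arm test that either document states outright

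*Protocol*

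**What the plan says.** **Design.** Protocol section 4b says that "eligible participants will be randomized to receive either A-tDCS (1 mA) or sham-tDCS (placebo) for 15 sessions", so each participant has one assignment throughout. Section 4c adds: "Subjects will be randomized 1:1 (A-tDCS: S-tDCS), controlling for clinical center, aphasia type, and severity". That balances covariates across arms; it does not form matched pairs.

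**Test for secondary outcomes.** Protocol 7b and the Secondary Analyses part of 7c both ask for mean change by arm with 95% confidence intervals for interval-scale variables, followed by: "Treatment comparisons will be made with a paired t- test". The outcomes introduced in those sections include error types: "We will examine changes in types of naming errors (defined by the PNT) by tDCS treatment group".

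**Primary outcome, for contrast.** Under Statistical Analysis in 7c: "The primary analysis will compare change in accuracy of naming untrained items between groups (A-tDCS versus sham) in a two-sample" t-test.

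**SAP.** Section 2 says that the final SAP "will trump the protocol". Section 10 gives a repeated-measures mixed model with arm, visit and their interaction for continuous measures in a named list: discourse features, Content Units, syllables per Content Unit, HANA, NIHSS, SIS, mRS and PHQ-9. Error types are not listed. They appear in 8.2: "Naming errors will also be analyzed and categorized as semantic related, semantic unrelated", followed by further categories but no test or model.

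**The concern.** A paired t-test needs a natural link between the two values in each pair. In this trial the link exists only within a participant, before against after, and not between a participant on active stimulation and one on sham. The sentence can therefore be read in two ways, and neither works.

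- **Between arms.** Someone must decide who is paired with whom. The p-value then depends on a choice that the protocol does not specify, and unpaired participants drop out if the arms differ in size.
- **Within each arm.** The test asks whether naming changed from baseline. These patients are within three months of stroke and both arms receive therapy, so change is expected without any stimulation effect. Significance in one arm but not in the other says little about the difference between arms.

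At stake is the between-arm result for one family of secondary outcomes, the naming-error types, and the consistency of the protocol with its own primary test.

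**Working it through.** **1. Where the sentence still has force.**

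| Outcome | Between-arm method in the SAP | Is the paired t-test still the only explicit one? |
|---|---|---|
| Primary (PNT correct) | Multiple regression adjusted for aphasia type, AQ and age (8.2) | No; it never applied |
| Outcomes listed in section 10 (continuous measures) | Mixed model | No; superseded |
| Trained items | Same approach as the primary (8.2) | No |
| Naming-error types | None named (8.2) | Yes |

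The protocol's longitudinal model (7c, Post-Testing Phase) does not fill the last row. Its use for other secondary outcomes is optional, and its listed independent variables are time, aphasia type, severity and center, without an arm term.

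**2. Inputs.** From Sample Size Determination in Protocol 7c: 20 per arm, difference 23, sham change 10, SD of change 22.2, two-sided alpha 0.05, and 40 to 45 completers expected out of 50. These are primary-outcome planning values. Neither document gives a mean or SD for any error type, so steps 4 to 6 borrow the SD as an assumption.

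**3. The plan's own figure.** Standard error of the difference = 22.2 × √(2/20) = 7.02. Noncentrality = 23/7.02 = 3.28. With 38 degrees of freedom (critical t 2.024), the noncentral t gives power of 89.1%. The stated 89% reproduces.

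**4. Arbitrary pairing, effect on power.** With independent arms the standard error stays at 7.02, but the degrees of freedom fall to 19 (critical t 2.093). Power is 87.4%, a loss of 1.7 points. In addition, any odd number of completers (41, 43 or 45) makes the arms unequal, so at least one person cannot be paired.

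**5. Arbitrary pairing, effect on the p-value.** I took one simulated data set with 20 per arm, SD 22.2 in each arm and an observed difference of 15. The two-sample test gives t = 15/7.02 = 2.14 and p = 0.039. Over 10,000 random pairings of the same data, the central 95% of paired p-values ran from 0.010 to 0.091, and 57% were below 0.05.

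**6. Within-arm tests with no treatment effect.** Standard error of a mean change = 22.2/√20 = 4.96, with 19 degrees of freedom. Let p be the chance that one arm is significant for improvement when both arms have the same true gain. Exactly one arm is significant with probability 2p(1 − p).

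| True gain in both arms | Gain/4.96 | p | 2p(1 − p) |
|---|---|---|---|
| 5 | 1.01 | 15.8% | 27% |
| 10 | 2.01 | 48.1% | 50% |
| 15 | 3.02 | 81.8% | 30% |

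The expression cannot exceed 50%, so the middle row is at the ceiling. With no drift at all, p is the test's own 5% and the split is 2 × 0.05 × 0.95 = 9.5%.

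**The case against.** The strongest reply is that the SAP governs. Its final version is to define every pre-specified analysis and override the protocol, and the paired t-test appears nowhere in it. SAP 8.2 takes up naming errors between a sentence applying the primary approach to trained items and one adding covariates to the primary model, so regression is a natural reading. This largely stands. A reader might infer that the paired test governs all secondary outcomes, or that it definitely governs error types; the documents support neither. What remains is that the phrase about using the same approach is attached to trained items only. The intended model for error types has to be guessed, and the one test actually written down is wrong for the design.

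A second reply is that the illustration concerns a different outcome. That also stands: error counts need not drift as total accuracy does, and some types may rise as non-responses fall. A reader might take 50% as this trial's false-positive rate. It is the ceiling of the formula, reached near one assumed gain, and neither document plans to claim efficacy from contrasting within-arm results.

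A third reply is that pairing would suit a crossover, and parts of protocol section 4 do mention more than one treatment period. A reader might infer a crossover design. The randomisation text rules this out, since each participant has a single assignment for all 15 sessions.

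Finally, secondary outcomes are called exploratory in the protocol and supportive in the SAP, which limits the consequences.

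**Conclusion.** Wrong as written; minor severity. A paired t-test is not a valid comparison of these two arms, and the protocol states it twice while using a two-sample test for its primary outcome. Because SAP section 10 supersedes it for the outcomes listed there, the live gap is confined to PNT naming-error types, for which no valid between-arm method is explicitly stated.

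A reader might infer that the primary result, the sample size or the decision on a Phase III study is compromised. None of these rests on the paired test.

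The size is illustrative only and rests on carrying the SD of 22.2 and 20 per arm over to error counts: a split verdict in about 27% to 50% of trials for equal gains of 5 to 15 if the test is run within arms, and a power loss of under 2 points if arms are paired arbitrarily. The stronger objection to arbitrary pairing is that the p-value then depends on an unspecified choice. That the test does not fit the design needs no numerical assumption.

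**What to change.** 1. In Protocol 7b and 7c, replace the paired t-test with an independent-groups comparison of change, deferring to SAP section 10 for the outcomes listed there.
2. In SAP 8.2, add one clause: change in each naming-error type is compared between arms with the same covariate-adjusted regression as the primary outcome (arm, aphasia type, AQ, age). Another independent-groups model would also do, for instance one better suited to counts, provided it is stated.
3. Leave the primary analysis unchanged. The clause should cover naming errors only: a blanket rule placing every between-arm comparison under the section 10 model would conflict with the regression and multiple imputation that SAP 8.2 and 8.5 set for the primary outcome.

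The cost is one sentence in two places and one added clause, with no new data and no change to the sample size. SAP section 2 already provides for an update before database lock and unblinding, so the change can be made then.

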1. LIST OF ACRONYMS

- A-tDCS Anodal transcranial direct current stimulation
- AE Adverse Event
- AQ Aphasia Quotient
- ASRS Apraxia of Speech Rating Scale
- BNT Boston Naming Test
- CU Content Units
- DCU Data Coordination Unit
- fMRI functional Magnetic Resonance Imaging
- HANA Hopkins Action Naming Assessment
- mITT Modified Intent-to-Treat
- MRI Magnetic Resonance Imaging
- MEDdra Medical Dictionary for Regulatory Activities
- mRS modified Rankin Scale
- NIHSS National Institute of Health Stroke Score
- PNT Philadelphia Naming Test
- PPTT Pyramids and Palm Trees Test
- S-tDCS Sham transcranial direct current stimulation
- SAE Serious Adverse Event
- SALT Speech and Language Therapy
- SAP Statistical Analysis Plan
- SIS-16 Stroke Impact Scale -16
- SLP Speech Language Pathologist
- WAB-R Western Aphasia Battery- Revised
- WebDCUTM Web-based Clinical Trial Management System

